Procedures: 
At specific time points as outlined in the schedule of assessments, subjects will undergo the following assessments/procedures: collection of informed consent, general medical history including previous treatments for lymphoma, physical exam including vital signs and performance status, blood draws for complete blood count (CBC), chemistry panels, cytokines, C-reactive protein, lymphocyte subsets, anti-axicabtagene ciloleucel antibodies, and anti-CD19 CAR T cell analysis. Women of childbearing potential will undergo a urine or serum pregnancy test prior to radiotherapy as per standard protocol.
	

Subjects will also undergo a biopsy (core needle biopsy, or if not possible, FNA) shortly following RT. Subjects will also undergo a PET/CT as standard of care to assess response to RT about 6 months after CAR T infusion. If there is evidence for complete response on the 6 month PET/CT scan, patients will have an additional PET/CT scan at 12 months after CAR T infusion to assess for continued complete response. Otherwise, patients will need further work-up regarding 6 month PET/CT scan.

Routinely throughout the conduct of the study, subjects will be asked to report concomitant medications and adverse events and will have their disease assessed.

Methodology/Study Design:

This is a pilot study evaluating the feasibility, safety, efficacy, and toxicity of radiotherapy in patients with hematologic malignancies who will undergo any CD19-targeted CAR T cell therapy

Pilot Study

The pilot study will enroll approximately **20** subjects with refractory hematologic malignancies following CAR T cell therapy.

Each subject will proceed through the following study periods:

- Screening
- Enrollment
- RT simulation, planning, and treatment
- Biopsy following RT (on protocol)
- Post treatment assessment period with a PET/CT following RT (as standard of care)
- Long term follow-up period

For study requirements assigned to each study period, refer to Section 7 for details.

Long-term Follow-up

All subjects who complete the study, and those who withdraw from the study after receiving RT for reasons other than death, will be asked to participate in a long-term follow-up study for up to 6 months after their RT, with a focus on long-term efficacy and safety. These patients will also have long-term follow-up as part of CAR T cell therapy registry. After Month 24 patients will be followed via the CIBMTR immune effector cell therapy registry.

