9.7.5 Long-term Follow-up Period

All subjects who complete the study, and those who withdraw from the study after receiving RT for reasons other than death, will be asked to participate in the long-term follow-up portion of this study up to 12 months from CAR-T infusion, with a focus on long-term efficacy and safety. These patients will also have long-term follow-up as part of the FDA mandated CIBMTR CAR T cell therapy registry.

The following procedures will be completed for subjects who are enrolled at the time points of 6, 9, and 12 months following CAR-T infusion, as outlined in the SOA (Long-term Follow-up Period) Table 3:

- Physical exam
- CTCAE/PRO-CTCAE Surveys
- PET-CT/ Disease assessment at 6 and 12 months per standard of care
- Survival status
- Labs
 - CBC with differential
 - Cytokine levels
 - Lymphocyte subsets
 - Translational lab collection.
- Subsequent therapy for the treatment of NHL
- **Refer to Sections 8.4** for targeted adverse/serious adverse event reporting
 - Including neurological, hematological, infections, autoimmune disorders, and secondary malignancies
- Targeted concomitant medication documentation (for 12 months or until disease progression, whichever occurs first)
 - Including gammaglobulins, immunosuppressive drugs, anti-infectives, and vaccinations

Subjects may be contacted by telephone to confirm survival status and report targeted concomitant medication use.

If a subject progress in the LTFU phase, the subject will continue to be followed for survival status and subsequent therapy for the treatment of NHL. A translational lab sample and **serum (for cytokine evaluation)** should be collected at the time of progression as part of CAR T cell therapy protocol, prior to starting any subsequent anti-cancer therapy.

Should the subject fail to return to the clinic for a scheduled protocol specific visit, sites will need to make 2 attempts by a combination of telephone and mail to contact the subject. Sites must document both attempts to contact the subject. If a subject does not respond within 1 month after the second contact the subject will be considered lost to follow-up and no additional contact will be required.

As patients will be receiving commercial product, patients will also have long-term follow-up as part of FDA mandated CAR T cell therapy registry.

Table 2. Schedule of Assessments

Procedures	Screening	Enrollment & RT Planning	Radiotherapy		Post Radiotherapy Period			

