Blood draw for Cytokines ^{4,5}	X	X	X
Blood draw for translational lab collection ^{4,6}	X	X	X
Targeted AEs/SAEs ⁷	X	X	X
Targeted concomitant medication ⁸	X	X	X
Subsequent therapy for NHL ⁹	X	X	X

¹ PET-CTs/disease assessments will continue through Month 12 or until disease progression, whichever comes first, as is performed per standard of care.

³ Subjects will continue to provide samples for CBC w/diffs, lymphocyte subsets and anti-CD19 CAR T cells through Month 12 as per standard of care

⁴ Monthly starting 6 months from CAR-T infusion

⁵ Cytokines: 5cc red top tubes

⁶ Translational Labs: Two 10cc purple top tubes

⁷ Targeted AEs/SAEs will be collected for 24 months or until disease progression (whichever occurs first)

⁸ Targeted concomitant medications will be collected for 24 months or until disease progression (whichever occurs first)

⁹ Subsequent therapy administered after CAR-T infusion for a subjects' disease such as non-study specified chemotherapy, immunotherapy, targeted agents, as well as stem cell transplant must be collected until subject completes the long term follow up period, is considered lost to follow up, withdraws consent, or dies. Subjects may be contacted by telephone to collect information about subsequent therapy for NHL and to assess survival status.

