12.1 Study Endpoints

Primary Endpoint:

- Rate and severity of RT-related toxicity as per CTCAE v5.0 criteria during RT or within the first 30 days of completing RT.

Secondary Endpoints:

- **Duration of response (DOR):** Among subjects who experience an objective response, DOR is defined as the date of their first objective response (which is subsequently confirmed) to disease progression per Lugano criteria¹ or death regardless of cause. Subjects not meeting the criteria for progression or death by the analysis data cutoff date will be censored at their last evaluable disease assessment date and their response will be noted as ongoing.
- **Objective response rate (ORR) per IRRC:** ORR per IRRC is defined as the incidence of either a complete response or a partial response by Lugano criteria¹ as determined by the IRRC. All subjects that do not meet the criteria for an objective response by the analysis data cutoff date will be considered non-responders.
- **Progression-free Survival (PFS):** PFS is defined as the time from RT completion date to the date of disease progression per Lugano criteria¹ or death from any cause. Subjects not meeting the criteria for progression by the analysis data cutoff date will be censored at their last evaluable disease assessment date.

- **Overall survival (OS):** OS is defined as the time from RT completion to the date of death. Subjects who have not died by the analysis data cutoff date will be censored at their last contact date.

Exploratory Endpoints:

- Levels of anti-CD19 CAR T cells in blood
- Levels of cytokines in serum
- Incidence of anti-axicabtagene ciloleucel antibodies
- Investigation of potential biomarker development based on assessment of blood cells, tumor cells and the proposed actions of the investigational product.

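### DOR counts only responses that are later confirmed, while ORR does not; responders who relapse before confirmation drop out, so the relapse estimate in 12.4 is biased low

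*Combined protocol and SAP*

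**What the plan says.** Section 12.1 states that, among responders, "DOR is defined as the date of their first objective response (which is subsequently confirmed) to disease progression" per Lugano or death from any cause. Patients without an event "will be censored at their last evaluable disease assessment date and their response will be noted as ongoing". No method, minimum interval or deadline for confirmation is given.

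The same section states that "ORR per IRRC is defined as the incidence of either a complete response or a partial response by Lugano criteria" as judged by the IRRC, with no confirmation step. The Lugano table in Appendix B has none either.

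On imaging, Table 2 marks PET-CT at screening only. Section 9.7.5 lists "PET-CT/ Disease assessment at 6 and 12 months per standard of care", counted from CAR-T infusion, and Table 3, footnote 1, adds that "PET-CTs/disease assessments will continue through Month 12 or until disease progression, whichever comes first". The synopsis (Procedures) is narrower: "If there is evidence for complete response on the 6 month PET/CT scan, patients will have an additional PET/CT scan at 12 months" after infusion. For everyone else it says: "Otherwise, patients will need further work-up regarding 6 month PET/CT scan". Section 10.1 provides for further PET-CT under standard care, without number or timing, and for off-schedule evaluation when symptoms suggest progression.

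Section 12.4 analyses DOR as the cumulative incidence of relapse, with non-disease death as the competing risk, reported every three months. Section 12.5 plans a comparison of the efficacy endpoints with historical controls who had no RT.

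**The concern.** A duration endpoint should follow every responder from the moment of response. Here a patient enters the DOR set only by remaining in response until some later confirmation. Staying in response is what DOR is meant to measure, so the set is selected on its own outcome. The interval between first response and confirmation becomes guaranteed relapse-free time, and a relapse inside it removes the patient instead of counting as an event.

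Two things follow. DOR and ORR describe different patients, so a reader cannot take the ORR responders and ask how long those responses lasted. And the relapse curve errs towards durability. Durability matters in this setting: section 3.2.1 says about 60% of CAR-T patients eventually relapse. In the comparison planned in 12.5, guaranteed relapse-free time would favour RT unless the controls were selected in the same way.

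**Working it through.** **The plan's own figures.** The documents give no figure for response rate, relapse or DOR. The one computed design figure, 19 patients in 12.2, does reproduce: 1.96² × 0.5 × 0.5 / 0.10² = 96.04, and 96.04 / (1 + 95.04/24) = 19.4. It does not enter DOR.

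**Step 1: what the schedule can confirm.**
- Response first seen at Month 6: the only later scheduled scan is Month 12. A patient still in response there is confirmed. A patient who relapses before or at that scan is not.
- Response first seen at Month 12: no later scan is scheduled. The patient counts in ORR but is not confirmed on schedule.
- Partial response at Month 6: 9.7.5 and Table 3 list a Month 12 scan without a complete-response condition. The synopsis schedules it for complete responders and sends the others to work-up of unstated content.

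**Step 2: size of the bias at 6 months.** Assumptions, not in the documents: response is first seen at Month 6, time to relapse is exponential, and the true 6-month relapse probability q among responders is 20%, 40% or 60%. If every response is confirmed m months after Month 6, only patients relapse-free at m are kept, and the apparent 6-month relapse is

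1 − (1 − q)^((6 − m)/6).

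For q = 0.40 and m = 3: 1 − 0.60^0.5 = 1 − 0.7746 = 0.2254.

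| How a Month 6 response is confirmed | q = 20% | q = 40% | q = 60% |
|---|---|---|---|
| No condition, all responders | 20% | 40% | 60% |
| Unscheduled scan 1 month later | 17% | 35% | 53% |
| Unscheduled scan 3 months later | 11% | 23% | 37% |
| Month 12 scan only | 0% | 0% | 0% |

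**Step 3: a mixture.** Let a share f of responders have a scan at 3 months and the rest be confirmed only at Month 12. With q = 40%, the apparent relapse is f(0.7746 − 0.60) / [0.7746f + 0.60(1 − f)]. For f = 25% this is 0.0437/0.6437 = 6.8%; for f = 50%, 0.0873/0.6873 = 12.7%.

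**Step 4: in patient numbers (assumed).** Suppose 8 of 20 patients respond at Month 6. If 4 relapse by Month 12, relapse among all responders is 4/8 = 50% (exact 95% CI 15.7 to 84.3%). On scheduled scans the DOR set is the other 4, with 0/4 (CI 0 to 60.2%). If 2 relapse, 2/8 = 25% (3.2 to 65.1%) becomes 0/6 (0 to 45.9%).

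**Step 5: the 3-month time point.** On scheduled scans alone, a Month 6 responder is next imaged about 6 months later, so a relapse found there is dated at about 6 months. The 3-month figure is therefore near zero with or without the confirmation condition. Scan spacing causes that, and the change proposed here does not repair it.

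**The case against.** A reader might infer that DOR must show almost no relapse by construction. The documents do not support that. Nothing ties confirmation to the Month 12 scan. Section 10.1 says further standard-care PET-CT will take place; such a scan could confirm a Month 6 response early, or show a response before Month 6 that the Month 6 scan then confirms. Deaths after confirmation, and relapses found through symptoms after Month 12, still end DOR. This part of the objection stands: zero is the limit when only scheduled scans confirm. It does not remove the bias, because any later confirmation requirement works in the same direction (Steps 2 and 3).

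A reader might also infer that a Month 6 partial response cannot be confirmed under the synopsis. That too goes beyond the text: such a patient has no scheduled confirming PET there, but the unspecified work-up might supply one.

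Confirmation could instead mean central review of the same scan, since 10.1 has the site investigator assess response and 12.1 has the IRRC determine ORR. That reading would remove no early relapse. The text does not settle it. If it is what was meant, deleting the condition costs nothing, because ORR already rests on the IRRC.

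Early relapses are not lost to the trial. PFS runs from RT completion, has no confirmation condition and is reported every three months. Requiring confirmation is also a legitimate choice in itself, and the synopsis eligibility criteria show that the protocol is alert to misleading PET findings. But the plan does not require it for ORR, and it does not define it for DOR.

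**Conclusion.** The point holds as a bias of known direction and uncertain size. Unless confirmation means review of the same scan, responders who relapse before confirmation count in ORR and vanish from DOR, and the cumulative incidence of relapse is too low. At 6 months from response it is 0% if only scheduled scans confirm. It is nearer the truth, but still low, if unscheduled scans confirm sooner: 23% or 35% against an assumed 40%. The relapse rates, the exponential form, the response counts and the timing of unscheduled scans are all assumptions; the direction does not depend on them.

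The consequence is modest. DOR is secondary and descriptive in a pilot of about 20 patients, and no interim efficacy rule uses it. The planned historical comparison is the main reason to correct it.

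**What to change.** In 12.1, delete the parenthetical confirmation condition from the DOR definition, so that DOR runs from the first documented complete or partial response in every patient counted as a responder for ORR, and relapses before Month 12 count as events.

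Reconcile the synopsis (Procedures) with 9.7.5 and Table 3 on which patients have the Month 12 PET-CT. This matters for DOR: a Month 6 partial responder with no later assessment and no recorded event would be censored at the date of response and contribute no follow-up.

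The cost is one phrase in 12.1 and one reconciled sentence; the DOR change needs no scan beyond those in Table 3. The downside is small: reported DOR will be shorter, and some single-scan responses that later prove false will be included. If the sponsor prefers to keep confirmation, the alternative is to define its method, minimum interval and window, report the unconfirmed responders and those who relapsed before confirmation, and use a landmark analysis from the confirmation time.

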6.3 Excluded Medications

Corticosteroids and other immunosuppressive drugs should also be avoided for 3 months after CAR T cell administration, unless used to manage CAR T cell-related toxicities. Other medications that might interfere with the evaluation of the investigational product, such as non-steroidal anti-inflammatory agents should also be avoided for the same time period unless medically necessary. Physiologic steroids (less than or equal to 5mg/day) will be allowed on study.

Treatment for lymphoma such as chemotherapy, immunotherapy, targeted agents, radiation, and high dose corticosteroid, other than defined/allowed in this protocol, and other investigational agents are prohibited, except as needed for treatment of disease progression after the CAR T cell infusion and radiation therapy. Patients will be allowed to remain on maintenance therapy (ibrutinib, revlimid, etc) if these medications were initiated prior to and continued during CAR-T infusion.

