6.4 Subsequent Therapy

Subsequent therapy administered after the CD19-targeted CAR T cell therapy infusion for a subject's disease, such as non-study specified chemotherapy, immunotherapy, targeted agents, as well as stem cell transplant and radiation therapy, will be recorded until the subject completes the long-term follow-up period, is considered lost to follow-up, withdraws consent, or dies.

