9.7.4 Post RT Period

Patients are seen weekly for one month following RT. Subject will allow study personnel to continue to access medical records so that information related to subjects health condition and initial treatment response may be obtained. The following procedures will be completed for subjects as outlined in the SOA:

Seven to fourteen days after beginning RT, patients will undergo a core-needle biopsy (FNA acceptable if core-needle unable to be done for any reason). This biopsy will allow a direct comparison of inflammatory cytokine and T cell infiltration into the tumor in comparison to pre-RT biopsy that confirmed refractory disease. If it is deemed unsafe to proceed biopsy may be deferred as other immune correlates will be collected from peripheral blood and serum.

- Physical exam
- Vital signs, including blood pressure, heart rate, oxygen saturation, and temperature
- Labs
 - Chemistry Panel
 - CBC with differential
 - Cytokine levels
 - Lymphocyte subsets
 - Translational lab collection.
- Adverse/Serious Adverse Event reporting (refer to [Section 8](#) for safety reporting guidelines)
- Concomitant medications documentation

If a subject is admitted to the hospital with any **RT, CAR T-** related adverse event(s), the following labs will be collected **on the day of hospital re-admission and then weekly through and including on the day of discharge**:

- Translational labs (two 10cc purple top tubes)
- Cytokines (one 10cc red top tube)

At any time during the post treatment assessment period, if a subject progresses and is either not eligible for re-treatment or chooses not to pursue re-treatment, the subject will proceed directly to the Month 3 visit and be followed for survival, subsequent therapy and disease outcomes in the long term follow-up period. A translational lab set **and serum sample (for cytokine evaluation)** should be collected at the time of progression, prior to starting any subsequent anti-cancer therapy.

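### ORR in Section 12.1 has no stop at new anti-lymphoma therapy, so a response to treatment given after RT can be counted as a response to RT

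*Combined protocol and SAP*

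**What the plan says.** Section 12.1 states the endpoint: "ORR per IRRC is defined as the incidence of either a complete response or a partial response by Lugano criteria", as judged by the IRRC. The sentence that closes the definition is "All subjects that do not meet the criteria for an objective response by the analysis data cutoff date will be considered non-responders". No assessment window, deciding scan or rule for new therapy is given. Section 12.4 adds an exact 95% interval and no sensitivity analysis.

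On later treatment, 6.3 prohibits other lymphoma therapy "except as needed for treatment of disease progression after the CAR T cell infusion and radiation therapy". Section 6.4 says that subsequent therapy, including transplant and radiation, "will be recorded until the subject completes the long-term follow-up period, is considered lost to follow-up, withdraws consent, or dies". No efficacy analysis in Section 12 uses that record.

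Two places limit scanning. Table 3 footnote 1 says: "PET-CTs/disease assessments will continue through Month 12 or until disease progression, whichever comes first". Section 9.7.5 lists only survival and subsequent therapy as follow-up once a patient progresses in the long-term period.

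Section 9.7.4 is looser. A patient moves directly to the Month 3 visit "if a subject progresses and is either not eligible for re-treatment or chooses not to pursue re-treatment", and is then to "be followed for survival, subsequent therapy and disease outcomes in the long term follow-up period".

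**The concern.** ORR is meant to describe what RT achieves in disease that CAR T cells did not clear. With the data cutoff as its only limit, the definition does not separate a response to RT from a response to whatever was given next. Any error goes one way, because a later-therapy response can only raise the count.

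The endpoints can also contradict each other. A patient who progresses after RT and then responds to the next line is a PFS event and an ORR responder. That patient would also enter DOR, which runs from first response to progression, although a progression has already occurred. For safety the protocol does use new therapy as a boundary: under 7.4.1, reporting of non-serious adverse events stops when it begins. Efficacy has no matching rule.

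What is at stake is a descriptive figure. But 12.5 sets the efficacy results beside historical patients who had no RT, and 2.1 links a larger study to RT proving safe and effective.

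**Working it through.** **The plan's own figure.** No ORR target or precision is stated. The one calculation, 19 patients in 12.2, is not tied to ORR. It reproduces as one proportion with a finite population of 24 and a half-width of 10 points. With p = 0.5 (assumed), n0 = 1.96² × 0.25 / 0.10² = 96.04, and n = 96.04 / (1 + 95.04/24) = 19.4. With p = 0.3, n0 = 80.67 and n = 18.7. This point does not change it.

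**Which routes remain open.**

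1. *New therapy without documented progression.* The stop in Table 3 footnote 1 is triggered by progression, not by new therapy. Refractory disease is confirmed 30 to 90 days after infusion (4.1) and planning takes 7 to 14 days (9.7.2), so RT starts at about day 37 (30 + 7) to day 104 (90 + 14), later if screening adds time. The first scheduled response scan is at about 6 months from infusion, roughly day 183. The gap is 183 − 104 = 79 days to 183 − 37 = 146 days. Table 2 shows no PET in the four weeks after RT. A patient switched on clinical grounds in that gap would still have the Month 6 PET, and a CR or PR on it meets the definition.
2. *Off-schedule scans.* Section 10.1 provides for further standard-of-care PET-CT and for evaluation outside the schedule when symptoms suggest progression. Section 12.1 does not restrict ORR to scheduled scans.
3. *Re-treated progressors.* Section 9.7.4 moves on only progressors who are not re-treated, and still follows them for disease outcomes. It does not say that re-treated patients leave response assessment.

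**Size per patient.** With the planned n of 20, one reclassified patient is 1/20 = 5 points. Exact (Clopper-Pearson) limits are the 0.025 quantile of Beta(x, n − x + 1) and the 0.975 quantile of Beta(x + 1, n − x). The counts below are illustrative.

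| Responders | ORR | Exact 95% CI |
|---|---|---|
| 6/20 | 30% | 11.9 to 54.3% |
| 7/20 | 35% | 15.4 to 59.2% |
| 8/20 | 40% | 19.1 to 63.9% |

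**Possible range.** Let r be the true ORR to RT, s the share of RT non-responders who get further therapy and are scanned again by the cutoff, and q the response rate to that therapy. Reported ORR = r + (1 − r) × s × q. The values of r and s are assumptions. The values of q (14%, 18%, 26%) come from the refractory-lymphoma chemotherapy results in 3.1 and serve only to size the effect.

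- Low: r = 50%, s = 25%, q = 14% gives 50% + 1.75 = 51.75%.
- Middle: r = 30%, s = 50%, q = 18% gives 30% + 6.3 = 36.3%, or 1.26 extra responders in 20.
- High: r = 20%, s = 100%, q = 26% gives 20% + 20.8 = 40.8%.

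Because scheduled scans end at progression, low s is the more plausible end. At s = 25%, with r from 20% to 50%, the excess is 0.35 to 1.04 patients in 20.

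**The case against.** The strongest reply is that the plan rarely creates the scan on which a later-therapy response could be read. Scheduled assessment ends at progression, and 9.7.5 then lists no response assessment. The synopsis treats the 6-month PET/CT as the scan for response to RT and gives a 12-month scan only to complete responders. Section 6.3 permits new therapy only for progression, so a switch without progression would usually be a deviation. The re-treatment route is read from what 9.7.4 leaves unsaid, and that term is undefined.

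Much of this stands, and it is why the number affected is probably small. It does not close the gap. These are visit-schedule rules and not part of the endpoint. Section 6.3 does not require Lugano-documented progression before a switch. A deviation does not remove a treated patient from ORR.

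A second reply concerns the remedy. Section 3.2.1 reports that 10-15% of patients with PR, SD or PD at day 30 later convert to CR. Stopping the count at first progression could therefore discard genuine delayed responses. That is right, and the cut should be at new therapy instead.

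A reader might infer that the plan deliberately counts next-line responses. It does not say so: the sentence on non-responders is itself conservative, and the problem arises from a missing exclusion. A reader might also take ORR for the main efficacy result. It is one of four unranked secondary endpoints, with no test or decision rule.

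**Conclusion.** The concern holds in a limited form. As worded, ORR accepts any CR or PR up to the data cutoff, whatever treatment preceded it, so a response to therapy given after RT can be reported as a response to RT. The schedule narrows this to three routes and does not remove it.

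Each affected patient adds 5 points at n = 20. The documents do not give the number affected. The move from 6/20 to 8/20 is an illustration, and the modelled excess of about 2 to 21 points rests on assumed inputs, with the lower end more plausible.

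It would go too far to conclude that the comparison in 12.5 must favour RT. The documents do not say how response was counted in the historical patients, so the net bias of the comparison is unknown. What can be said is that the RT side can only be raised. For a descriptive secondary endpoint this is a moderate matter, worth correcting because the correction is small.

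**What to change.** In 12.1, define ORR as the best Lugano CR or PR relative to the pre-RT PET-CT, assessed after RT and before the start of any subsequent anti-lymphoma therapy, including transplant and non-study radiation. Count all other treated patients as non-responders. State that study RT, and maintenance therapy continued as 6.3 allows, are not subsequent therapy; this is needed because the record in 6.4 opens at CAR T infusion.

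Show on a separate line any response that follows a Lugano progression without new therapy, so that delayed responses are neither lost nor hidden. Keep the any-time ORR as a sensitivity analysis.

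Cost: a short change to 12.1 and a matching line in 12.4, with no new visit and no change in sample size. ORR may be slightly lower. Sections 6.4 and Table 3 already require a record of subsequent therapy but do not mention its start date, so that date must be added. Table 3 footnote 9 also omits radiation, which 6.4 includes, and the two should be aligned.
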